Appendix III: App specifications

General use case description:

- I. A newly diagnosed HIV-positive patient with Android smartphone will be enrolled to the SmartLtC study by study staff and randomised to receive the smartphone app or not. Upon being randomised to smartphone app arm, the study staff member will install the app on the phone through a USB cable connection, (or through a Library Box - <http://librarybox.us/whatis.php>). The app icon and name will not refer to health or medicine in any way to ensure privacy for the user.
- II. Once app has been installed patient will create username and password, and select PIN code. The app can then be accessed immediately which will provide access to “More information” and “FAQ’s” (Frequently Asked Questions)⁵ sections, but will not include lab results. The study staff member will provide the patient with a brief training session on use of the app. Patients will be informed that they can read “More information” and “FAQ” sections at any time, but laboratory results will only be displayed after they have been received. All past results will be accessible to the patients and displayed along with any new results.
- III. When a CD4 count/Viral Load (VL) result is received by the NHLS database an App-based notification will show on the patient's screen informing them new information is available and to open the app. (Suggested text for the app-based notification “You have new information waiting. Please open the app”.) Once the patient opens the app and enter their PIN code (which is verified by the server) their CD4/VL result is shown under “Lab results” in the app. The CD4 count/VL results will be written in red, yellow or green to highlight the relative immediacy of action needed by the patient.
- IV. If the patient selects a CD4 count number (to be a suggested action on screen), a pop-up screen will provide a basic explanation of what that CD4 count means and what action they need to take. (Note: The numerical text will be coloured and the pop-up screen will also display a visual-analogue scale going from red to yellow to green, with a marker showing where the patient's CD4 count sits along the scale.) At the bottom of the pop-up will be a link to more detailed information about HIV and laboratory results. On every screen will be a link to a help page which displays the contact number for the National AIDS Helpline and the study coordinator.
- V. HIV-positive patients require life-long care and treatment. For follow-up care, the app will notify the patient that it is almost time to attend a follow-up blood test (at both 5.5 months and 6 months after the first CD4 count result has been received). Patients will attend the clinic for a second blood test (the follow-up CD4 counts or VL) at the 6 month mark. The app will connect to the results server daily at this point until there is a new laboratory result in the database. When the app received the new lab result the app will create another notification for the patient to check their results through the app.
- VI. Regular 6 month or 1 year (depending on patient's most recent CD4 count) blood tests must be done. The app will create reminder notifications, ping the

⁵ Note: Wits RHI to supply medical content for the “More information” and “FAQ’s”.

server for results soon afterwards, and notify the patient when the results are received.

- VII. App analytics on use is to be collected within the app. This will include patient use of the app such as length of time app is open, number of times app opened, which screens were seen, number of unsuccessful and successful lab result collections, number of incorrect username/password or PIN errors etc.

A tabular overview of app requirements is available below:

Platform	Android smartphone running Gingerbread or higher
Deployment	On-site USB/Wi-Fi (LibraryBox) install by research staff
Use of Smartphone App	
 - Patient registration will occur at clinic site with study staff member; Demographic information, photo ID and lab ID required. - Patient will receive an Android notification through their app on their phone when new CD4/VL result is in NHLS database - Patient can view CD4 results (new and historical) on app 
 - NB: CD4 and VL results are colour-coded (red, yellow, green) based on 
 - CD4 level: yellow >500, red < 501 - VL: green below 1001, red above 1000 - Patient can select individual results which will open up an information box explaining what that result means along with a visual-analogue scale showing green to yellow to red and where the patient's CD4 count or viral load sits on the scale - Patient offered FAQ and information sections to learn more about HIV ('basics'. 'signs and symptoms of co-infection, 'sex and hiv'), laboratory results, online resources, and contact information (National AIDS helpline) - Contact numbers (study coordinator, SA AIDS helpline) and 3rd party HIV-related websites provided in app help - Patient to receive further Android notification at 5.5 months and 6 months after app installation to remind about upcoming visit to clinic for additional blood test.
Authorization & Authentication	
At first use:
 
 - Patient to create username (e-mail address?) and password connected to SA ID/Passport number/Refugee number & Lab Requisition ID 
Notes:
 
 - Must create or connect to NHLS database for results! - Server-side user creation 
At subsequent use:
 
 - PIN required at every use of app (similar to Standard Bank android app) 
 - Server-side PIN authentication - PIN and/or password change possible (how?)

App & data security	
Network
 
 - All passwords and patient data encrypted 
App
 
 - All app data to be encrypted - PIN not stored locally
Main screens	
 - Login: UN/PW - PIN code - Lab results - More information - FAQ - Help me (available from any screen)
Notifications or Alerts (to patient)	
App-based notification when:
 
 - Patient joins study: Welcome message - New patient laboratory result arrives to phone from lab database: Notification of new information - It is time for patient to return to clinic for blood test (reminders; early notification at 5.5 months, regular notification at 6 months): Reminder to attend clinic 
Note:
 
 - Notifications created by app based on time passed and results available
Patient enrolment details (to link to NHLS database)	
 - First name - Last name - SA ID, passport or refugee number - DOB (if no SA ID number) - Gender - Lab requisition ID of blood specimen
Important contact information	
Help icon displayed at bottom of every screen (even login) to allow for easy access to support. Selecting icon will provide a list of support numbers (study coordinator, SA AIDS helpline) and 3rd party HIV-related websites

Analytics	
All screens of the app should report to an analytics aggregator (Android Analytics?) to allow the study team to monitor app usage by user.

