The application will be able to be quickly installed by the study staff, at no cost to the patient, and once installed, will consume minimal network data, as patients are very conscious of cost of data bundles. For the study the app will be available on Android only (the type of phone potential participants with non-Android smartphones have will be recorded). The app icon and name on the phone will be non-descript and not suggestive of a health application. Username, password and PIN requirements will prevent any unauthorized access to this data. App-based push-notification reminders will notify patient when a new result is present by stating “*There is updated information for you. Please use the app to access it*”. The notification will give no detail about the nature of the information, ensuring all detail is only displayed within the password-protected section of the app.

Within the app, laboratory result data will be presented clearly, with simple explanations on every screen, in English and Zulu with a grade 4 reading level (as per WHO guidelines on literacy). Laboratory results will not be shown in isolation, but will be supplemented with

informative and relevant information explaining the result that has been shown³ and the recommended action for the patient to take. Patients will also be able to view additional HIV-related information and a Frequently Asked Questions (FAQ) through the app. This information will be created with support from HIV clinicians and psychosocial teams and focus on information that is relevant for newly diagnosed HIV-positive individuals. Links to external sites (e.g.: National Department of Health HIV site, LoveLife, etc.), to get further HIV support/information will be provided (to be opened in the smartphone web browser) and access to them will be monitored by the app. Automated prompts will be built-in to the app, triggered automatically at five and a half months, six months and 12 months after the app has been installed. These triggers will inform the patient that it is (almost) time to attend a further laboratory test.

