- Total annual per patient cost of providing a comprehensive model of ART linkage to care using the smartphone app (receiving laboratory results and linkage-to-care) plus cost over 10 years

Cost-effectiveness analysis involves the comparison of two or more competing methods in terms of both their costs and consequences. The outcome measure of the cost-effectiveness work will be the cost of ART initiation with a particular intervention in South African Rand (ZAR) per disability adjusted life year (DALY) averted. The lower the cost per DALY averted, the more cost-effective the intervention. It will be based on a 5% discount rate.

For each target and cost scenario, this analysis will be able to provide the estimated impact in terms of OI and AE averted, impact in HIV stage defined by CD4 count and treatment costs and deaths averted due to ART linkage to care of those using the smartphone app.

Participant opt-out

All participants will be provided with contact information for the study team and will be informed that they can drop out of the study at any time with no consequences (as per Good Clinical Practice guidelines). Should a participant request to withdraw from the study the team will identify their informed consent sheet and mark it accordingly, remove the patient's data from REDCap and notify the NHLS if they are part of the intervention arm to ensure they will not receive additional notifications of laboratory results. The participant will be asked if they would like to keep their username and password active to access the app in the future; their account will be deleted or kept accordingly.

Safety considerations

Accidental disclosure (through phone loss/theft/borrowing or any other method) will be limited by the study team as much as possible. This will be done actively by having a username, password AND PIN code for app use. Additionally, the recruitment team will inform participants of the sensitive information on the app and request that they don't share it with

anyone. Lastly, the app icon and name will not relate to health or HIV in any way; only after the username and password is entered will health-related terminology be used.

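### Appendix III makes the AIDS helpline and HIV websites reachable from the login screen, contrary to the protocol's own disclosure safeguard, and leaves reminder wording unstated

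*Protocol*

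**What the plan says.** The protocol's Safety considerations section names accidental disclosure through loss, theft or borrowing of the phone as a risk to be limited. Its controls are a username, password and PIN, a request that participants not share the app's content, and two statements about what an outsider can see: "the app icon and name will not relate to health or HIV in any way", and "only after the username and password is entered will health-related terminology be used". The same section then deals with access to help. At recruitment, participants are told that for HIV-related questions they can ring the helpline numbers displayed in the app.

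The App specifications section in the protocol body fixes a neutral text for the alert that a new result is present, and adds: "The notification will give no detail about the nature of the information".

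Appendix III describes the help function in three places:

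- Use-case item IV: "On every screen will be a link to a help page which displays the contact number for the National AIDS Helpline", together with the study coordinator's number.
- Table row on main screens: login and PIN are listed among the screens, and the help entry reads "Help me (available from any screen".
- Table row on important contact information: "Help icon displayed at bottom of every screen (even login) to allow for easy access to support". It continues: "Selecting icon will provide a list of support numbers (study coordinator, SA AIDS helpline) and 3rd party HIV-related websites".

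On reminders, the Use of Smartphone App row provides for a further "Android notification at 5.5 months and 6 months after app installation to remind about upcoming visit to clinic for additional blood test". The protocol body lists prompts at 5.5, 6 and 12 months. Neither place gives the text that appears on the phone.

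**The concern.** The safeguard and the specification describe different apps. The protocol's Timeline points the developer's sub-contract to Appendix III for specifications, so a developer who follows it will build the version that departs from Safety considerations. A neutral icon and name protect the participant only until somebody opens the app and taps help.

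What is at stake is the confidentiality of newly diagnosed people in one arm of the trial. The protocol's background section prefers an app to SMS partly because an SMS can be read by anyone with access to the phone, and HIV content available before login weakens that argument. The population survey in Appendix II asks whether the phone is shared. The inclusion criteria require only access to an Android smartphone with data, and sharing is not an exclusion.

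The reminders raise a related question. If their on-screen text mentioned a clinic or a blood test, health-related wording would appear before any login.

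**Working it through.** No alpha, power, rate or sample-size formula bears on this point, and the plan gives no figure to reproduce. The check is a comparison of texts, followed by a count of participants affected.

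**Help page**

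| Question | Safety considerations | Appendix III |
|---|---|---|
| Is health-related wording available before login? | No | Yes, through the help icon on the login screen |
| What can be reached? | Nothing health-related | AIDS helpline and HIV-related websites, plus the study coordinator |
| Is it one loose phrase? | – | No: use-case item IV, the main-screens row and the contact-information row agree |

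1. The words in parentheses in "Help icon displayed at bottom of every screen (even login) to allow for easy access to support" show that access before login was intended.
2. The login screen itself carries only the icon. The helpline and websites appear after one tap, with no username, password or PIN.
3. On later uses Appendix III asks for the PIN, so the PIN screen is the one a borrower would normally meet. Read literally, the safeguard mentions only username and password, so the exact contradiction is at the login screen. The help page is equally open at the PIN screen, although the PIN is one of the stated controls against disclosure.
4. Laboratory results stay behind the PIN throughout. What is exposed is general HIV material, not patient data.

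**Reminders**

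1. The neutral text in the protocol body is stated for the arrival of a new result. The suggested neutral text in Appendix III, item III, is also for a new result.
2. The notifications row of Appendix III gives reminders a separate label that mentions attending the clinic. This is a category, not a display text.
3. The body text and Appendix III say what a reminder is for, but not what it shows. A neutral alert that opens to detail inside the app would satisfy every passage, and so would an explicit one. The documents do not decide between them.

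**Number affected**

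- SAP, section 5: about 350 recruited. Assuming equal allocation, 350 / 2 = 175 in the app arm.
- Protocol, Sample Size: at least 1000 per arm, so at least 1000 in the app arm.
- Proportion of phones that others use: not given, so the number actually at risk can be anywhere from none to all of these.

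**The case against.** The best defence is that the help icon serves a safety purpose of its own. Safety considerations sets out two aims, protection from disclosure and access to help, and Appendix III gives easy access to support as the reason for the icon. A participant who has forgotten a PIN may need the helpline. This stands: the aims compete, and it would be wrong to say that disclosure is the only safety risk the protocol addresses. But the protocol does not weigh one against the other. It makes an unqualified promise in one place and specifies the opposite in another.

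It can also be said that the exposure is limited: only an icon at login, general resources rather than results, a neutral name, and participants warned about sensitive content. That is correct and bounds the harm, but it does not remove the contradiction. Appendix III also contains open questions and reads in places as a working document, and focus groups are planned before recruitment. Disclosure is not among the items listed for testing, however, and the Timeline treats the appendix as the developer's specification.

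Some stronger readings are tempting but not supported:

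- A reader might infer that the reminders breach the safeguard or reveal HIV status. Their display text is not given, the mock-up screens in Appendix IV were not available for this check, and a mention of a clinic or blood test would not by itself disclose HIV.
- A reader might infer that participants will uninstall the app or withdraw, diluting the treatment effect. The documents offer no evidence or range for this.
- A reader might infer that participants are diagnosed on the day of enrolment. The Recruitment section says only that they are approached after a confirmatory test and CD4 blood draw.

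**Conclusion.** The help-page contradiction is established by the text alone: an app built to Appendix III does not meet the promise in Safety considerations. It applies to every participant given the app, about 175 or at least 1000 depending on which planned size is used. The first figure assumes equal allocation. How often it would lead to actual disclosure cannot be estimated from the documents. It should be corrected because it concerns participant confidentiality and the remedy is cheap.

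The reminder point is a gap in the specification, not a demonstrated breach, and needs only a clarifying rule. Neither point affects the primary endpoint, the sample size or the analysis.

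**What to change.** 1. In Appendix III (use-case item IV and the rows on use of the app, main screens and important contact information), limit the help page reachable before login or PIN to a neutrally labelled study-team contact. Place the AIDS helpline and the HIV-related websites behind the PIN.
2. In Safety considerations, say that the PIN as well as the username and password must be passed before health-related wording appears. Say also that participants are given the helpline number at recruitment, since the section now relies on numbers shown in the app. This would also serve the control arm, which has no app. The consent pages were not available for this check and may already carry the number.
3. In the App specifications section and the notifications row of Appendix III, state that the no-detail rule covers the 5.5-, 6- and 12-month reminders. The reminder wording should be neutral but may differ from the result alert. Identical text would make the two indistinguishable, and prompting the return test is part of how the app is meant to work.

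The cost is small. A participant who is not logged in cannot reach the helpline through the app, which item 2 offsets. Reminder detail would be read after PIN entry, and because the PIN is checked by the server this needs a data connection. Before development this is an edit to the specification. The SAP, however, describes the app as created and patients as already randomised. If that is the position, the built app should first be checked against both texts, and any change would need an update on phones already enrolled.

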Appendix IV: App Mockup Screens

1. PURPOSE

To present the results of the SmartLtC study: Did the study show an improvement in linkage to care. Receiving HIV care and treatment will decrease HIV transmission rates, improve patient health and mortality rates.

2. RESEARCH QUESTION

Can a smartphone health application increase linkage to care in newly diagnosed HIV-positive patients in Johannesburg, South Africa: A multi-site randomised controlled trial

3. OBJECTIVES AND ENDPOINTS

3.1 Primary objective/s

- 3.1.1. To test whether linkage to HIV care (defined by attendance to a second blood test within 8 months) is improved in the intervention arm compared to the control arm

3.2 Secondary objective/s

- 3.2.1. To compare ART initiation rates between intervention and control arms.
- 3.2.2. To assess the feasibility and acceptability of receiving laboratory results to a personal smartphone.
- 3.2.3. To assess secondary effects from improved patient information, including return rates after falling out of care (assessed through routine patient record reviews), patient satisfaction (through face-to-face surveys at the 6-month follow-up visit and end of the study), and rates of additional blood tests (especially CD4 count, viral load).
- 3.2.4. To assess patient knowledge levels of their laboratory results.
- 3.2.5. To specifically look at 2 subgroups – men and young adults (18 to 25 years of age), who would particularly benefit from improved linkage to care.
- 3.2.6. To assess the performance of the app in clients with different levels of education and standard of living, and see if there are differences in clinical and usage outcomes
- 3.2.7. To evaluate differences in linkage-to-care, HIV-knowledge, adherence to medication (treatment patients only) and reported quality of life between wellness and treatment patients.
- 3.2.8. To assess the financial and economic costs of providing the SmartLtC smartphone app.
- 3.2.9. To determine the incremental cost, and cost-effectiveness of ART initiation link to the smartphone app (receiving laboratory results and linkage-to-care) as compared to the standard ART initiation.

3.3 Statement of null and alternate hypotheses

The analysis of will include the following test of hypothesis:

H_0 : $\mu_{\text{Attendance to a second NHLS blood test within 8 months (Control)}} = \mu_{\text{Attendance to a second NHLS blood test within 8 months (Intervention)}}$

H_A : $\mu_{\text{Attendance to a second NHLS blood test within 8 months (Control)}} \neq \mu_{\text{Attendance to a second NHLS blood test within 8 months (Intervention)}}$

STATISTICAL ANALYSIS PLAN

SmartLtC: Does an Android Smartphone App Increase Linkage To Care in Johannesburg

Acceptance of the H_A will be considered to be a successful demonstration of difference between the intervention and control arms

3.4 Primary outcome variable/s

3.4.1. Attendance to a second NHLS blood test within 8 months

3.5 Secondary outcome variable/s

3.5.1. Attendance to a second NHLS blood test

3.5.2. Length of time between first and second NHLS blood test

3.5.3. Attendance to a second NHLS blood test within 8 months

4. STUDY METHODS

4.1 Overall study design

4.1.1. A multisite randomised controlled trial (participating sites: Hillbrow Community Health Centre, Helen Joseph Hospital, 80 Albert Clinic and Yeoville Clinic)

